Patients will be followed for survival after the end of treatment (EoT) visit every 3 months for 12 months, or until withdrawal of consent, death, or the end of study (i.e., when the last patient in the study has been followed up on study treatment for at least 1 year, or completed at least 6 months of survival follow-up period after their last dose of study treatment, has withdrawn consent, has died, or has been lost to follow-up), whichever occurs first. End of treatment imaging will be performed ≤ 28 days after treatment discontinuation for patients who discontinue for reasons other than PD if their previous scan was performed >3 weeks before EoT.

After discontinuation of study treatment, patients will also be followed for safety 30 days after EoT and then every 3 months for 12 months and for PFS approximately every 3 months after EoT visit until PD, death or initiation of the subsequent anti-melanoma treatment (if a patient discontinues from the treatment due to reasons other than PD).

Statistical Methods:

CCI

Analysis Populations:

The modified intent-to-treat (mITT) population will consist of all patients who receive at least one dose of any study treatment.

The safety population will include all enrolled patients who receive at least 1 dose of both study drugs.

Efficacy Analyses:

The primary efficacy endpoint of ORR (proportion of patients who achieve CR or PR) will be analyzed for each arm separately on the modified intent-to-treat (mITT) population which consists of all enrolled patients who received any study treatment. Estimated ORR with 95% confidence interval (CI) will be summarized for each arm.

Analyses of other efficacy endpoints will be specified in Section 12 of the protocol and the Statistical Analysis Plan (SAP)

Safety Analysis:

Continual monitoring of safety data will be performed by the independent Data Safety Monitoring Board (DSMB). Adverse events and concomitant medications will be coded according to medical dictionary for regulatory activities (MedDRA) and WHO Drug, respectively. Safety analyses will be performed on the Safety Population and will be presented by actual treatment arm.

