3.2. Schedule of Assessments

Table 1: Schedule of Assessments for Study XPORT-MEL-033 (42-Day Cycle)

Activity/Assessment	Screening ^a D -28 to -1	Cycles* 1			Cycles* ≥ 2			EoT Visit ≤ 28 Days Post-Treatment Discontinuation	Follow-up Visit ^b	
		D1	D3±2D	D15/D29 ±3D	D1	D3±2D	D15/D29 ±3D		30 days after EoTVisit +7D	Every 3 months until 12 months ±14D
Procedures										
Informed Consent	X									
Inclusion/Exclusion	X									
Demographics	X									
Medical history	X									
Concomitant Medications Review	X	Continuous					X	X	X	
Prior Melanoma Therapy	X									
Eligibility confirmation by Sponsor ^c	X									
ECOG Daily Living Performance Score	X	X		X						
Nutritional Counselling	X	Throughout, as needed								
Vital signs including weight	X	X		X			X			
Physical Exam – full	X						X		X	
Physical Exam – symptom directed		X		X				X		
Adverse Events ^d		Continuous								
Telephone contact ^e			X					X	X	
Collection of information regarding antineoplastic therapy after EoT								X	X	
Laboratory										
Hematology and Serum Chemistry	X	X		X	X		X	X		

Activity/Assessment	Screening ^a	Cycles* 1			Cycles* ≥2			EoT Visit	Follow-up Visit ^b	
		D -28 to -1	D1	D3±2D	D15/D29 ±3D	D1	D3±2D	D15/D29 ±3D	≤28 Days Post-Treatment Discontinuation	30 days after EoTVisit +7D
LDH	X	X			X			X		
Pregnancy test ^f	X	X						X	X	
CCI										
Drug Administration										
Selinexor		Selinexor will be administered once weekly (Days 1, 8, 15, 22, 29, 36 of 42-day cycle)								
Pembrolizumab		Pembrolizumab will be administered on Day 1 once every 6 weeks								
Anti-tumor Activity										
Tumor assessment by CT or MRI Scan	X	Tumor assessment will be performed every 9 weeks for 6 months, then every 3 months thereafter						X		

CT = computed tomography; D = day; ECOG = Eastern Cooperative Oncology Group; EoT = end of treatment; FU = follow-up; hCG = human chorionic gonadotropin; LDH = lactate dehydrogenase; MRI = magnetic resonance imaging; PDn = pharmacodynamics

* Cycles are 6 weeks in length.

^a Procedures that are performed as part of standard of care should not be repeated if they are within the screening window and are done prior to signing the ICF.

^b After discontinuation of study treatment for reasons other than PD, disease assessments should continue to be performed every 3 months until progression, start of new therapy or withdrawal of consent.

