6.2. End of Treatment

The end of treatment (EoT) visit will occur \leq 28 days post-treatment discontinuation. After discontinuation of study treatment, patients will be followed for PFS approximately every 3 months after EoT visit until PD, death or initiation of the subsequent anti-melanoma treatment (if a patient discontinues from the treatment due to reasons other than PD), and for survival every 3 months after end of treatment visit for 12 months or until withdrawal of consent, death, or the end of study (i.e., when the last patient in the study has been followed up on study treatment for at least 1 year or

completed at least 6 months of survival follow-up period after their last dose of study treatment, has withdrawn consent, has died, or has been lost to follow-up) whichever occurs first.

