10.3. Efficacy Assessments

10.3.1. Response criteria

Computed Tomography (CT) or Magnetic Resonance Imaging (MRI)

Disease response is based on tumor measurement using CT scans or, MRI. Scans will be performed at Screening (Day -28 to Day -1) and every 9 weeks for 6 months, then every 3 months thereafter until confirmed PD, death or consent withdrawal occurs. Scans at the EoT visit should be performed for patients who discontinue for reasons other than documented PD, if previous imaging was more than 6 weeks old. The same scan modality should be used for all assessments.

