12.4.1.2. Secondary Endpoints

- Progression-free survival is defined as time from date of first treatment to the date of first confirmed PD, or death due to any cause, whichever occurs first. Median PFS with 95% CI will be summarized for each treatment arm.
- Overall survival is defined as time to death, from the date of first treatment. Median OS with 95% CI will be summarized for each treatment arm.
- Complete response rate is defined as proportion of patients who achieved a CR. The point estimate and an 95% exact CI of CRR will be provided for each treatment arm.
- Duration of response is defined as the duration of time from first occurrence of response \geq PR until the first date of PD or death due to any cause, whichever occurs first. Median DOR with 95% CI will be summarized for each treatment arm.
- Disease control rate is defined as the percentage of patients who have achieved CR, PR or stable disease. The point estimate and an 95% exact CI of DCR will be provided for each treatment arm.

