Note: Patients with a global deterioration of health status requiring discontinuation of treatment without objective evidence of disease progression at that time should be reported as “*symptomatic deterioration*”. Every effort should be made to document the objective progression even after discontinuation of treatment.

Method of Measurement

The same method of assessment and the same technique should be used to characterize each identified and reported lesion at baseline and during follow-up.

Clinical Lesions

Clinical lesions will only be considered measurable when they are superficial (e.g., skin nodules, palpable lymph nodes). For the case of skin lesions, documentation by color photography including a ruler to estimate the size of the lesion is recommended.

CT, MRI

CT and MRI might be the best currently available and reproducible methods to measure target lesions selected for response assessment. Conventional CT and MRI should be performed with cuts of 10 mm or less in slice thickness contiguously. Spiral CT should be performed using a 5 mm contiguous reconstruction algorithm. This applies to the chest, abdomen and pelvis. Head & neck and extremities usually require specific protocols.

Cytology, Histology

These techniques can be used to differentiate between PR and CR in rare cases (for example, residual lesions in tumor types such as germ cell tumors, where known residual benign tumors can remain). The cytological confirmation of the neoplastic origin of any effusion that appears or worsens during treatment when the measurable tumor has met criteria for response or stable disease

is mandatory to differentiate between response or stable disease (an effusion may be an adverse drug reaction of the treatment) and PD.

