1.3.2. Secondary Endpoints

- PFS, defined as time from date of first treatment to the date of first documented progressive disease (PD) or death due to any cause, whichever occurs first. Responses are assessed per RECIST 1.1.
- OS, defined as time to death, from the date of first treatment.
- Complete response rate (CRR), defined as proportion of patients who achieved a CR per RECIST 1.1.
- DOR, defined as the duration of time from first occurrence of response ≥PR until the first date of PD or death due to any cause, whichever occurs first. Responses are assessed per RECIST 1.1.
- DCR, defined as the percentage of patients who have achieved CR, PR or SD for a minimum of 12 weeks. Responses are assessed per RECIST 1.1.
- Safety and tolerability of study treatment will be evaluated based on AE reports, vital signs, clinical laboratory results, and physical examination findings, by the occurrence, nature, and severity of AEs as categorized by the Common Terminology Criteria for Adverse Events (CTCAE) v5.0.

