4.3.2.2. Analyses of Time to Event Secondary Endpoints

[figure not shown]
For each time to event secondary endpoint (PFS, OS and DOR), the number of patients with events, number of patients censored, estimates and 95% CI for the median of event time will be presented by treatment group.

[figure not shown]
Time-to-event will be plotted for each treatment group using the Kaplan-Meier method. The plot will include the number of patients at risk for each treatment group over time.

Table 4-2 PFS and DOR Outcome and Censoring Definitions

#	Situation	Date of event or censoring	Outcome
1	No baseline disease assessment	Date of first treatment	Censored
2	No adequate post-baseline disease status assessment unless death occurs prior to first post-baseline assessment	Date of first treatment	Censored
3	Documented PD without missing 2 or more consecutive assessments	Date of PD	Event
4	Death before documented PD and without missing 2 or more consecutive assessments	Date of death	Event
5	 No documented PD or death on or before Database cut Withdrawal of informed consent Lost to follow-up Date of discontinuation from treatment + 30 days Two or more consecutive missing assessments and the disease assessment result after the gap is PD¹ Start of new antineoplastic therapy, whichever occurs first 	Date of last adequate disease assessment prior to the events listed in the left column	Censored

^{1.} If disease assessment results after 2 or more consecutive missing assessments were not PD, the disease assessment gap will be ignored.

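### SAP Table 4-2 stops counting PFS and DOR events 30 days after treatment ends, before any of the protocol's 3-monthly post-treatment scans falls due

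*SAP*

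**What the plan says.** **SAP 4.3.2.2, Table 4-2 (PFS and DOR).** Row 5 covers patients without PD or death on or before the earliest of a list of cut-offs. The list includes database cut, withdrawal of consent, loss to follow-up, new antineoplastic therapy and "Date of discontinuation from treatment + 30 days". The outcome is censored. The date used is the last adequate disease assessment before the cut-off, so day 30 is the trigger and the censoring date is usually earlier. Rows 3 and 4 count PD and death as events provided two or more consecutive assessments were not missed. They carry no treatment-related limit, and the table states no order of precedence.

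**Protocol follow-up after treatment.** Section 6.2 says that "patients will be followed for PFS approximately every 3 months after EoT visit until PD, death or initiation of the subsequent anti-melanoma treatment" when treatment stops for a reason other than PD; the Synopsis says the same. Footnote b to the Schedule of Assessments adds: "After discontinuation of study treatment for reasons other than PD, disease assessments should continue to be performed every 3 months until progression". Section 10.3.1 runs scans "every 9 weeks for 6 months, then every 3 months thereafter until confirmed PD, death or consent withdrawal occurs". Appendix 1, on symptomatic deterioration, adds: "Every effort should be made to document the objective progression even after discontinuation of treatment".

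**Endpoint definitions.** Protocol 12.4.1.2 measures PFS from first treatment "to the date of first confirmed PD, or death due to any cause, whichever occurs first". SAP 1.3.2 measures DOR "until the first date of PD or death due to any cause, whichever occurs first". Neither is limited to time on treatment.

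**Declared changes.** Protocol section 12 says that changes from its planned analyses will be described in the SAP. SAP 1.6 lists none.

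**The concern.** The trial pays for scans whose stated purpose is PFS, and the censoring table then sets them aside. Deaths more than 30 days after stopping are set aside too, although both definitions count death from any cause.

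The patients affected are those who stop without PD: for toxicity, for clinical deterioration, by choice, or while in response. Those reasons may be related to prognosis, in which case the censoring is informative and the Kaplan-Meier estimate no longer describes the endpoint as defined.

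DOR is the most exposed because it rests on few patients. The Synopsis describes a patient in the earlier melanoma study who left treatment because of a CR. That patient was CPI-naive and so illustrates only the pattern. Under row 5 such a patient's DOR would end at the last scan before day 30 after stopping, however long the response lasted.

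The 30 days equals the safety treatment period in SAP section 5. The SAP gives no reason for applying it to an efficacy endpoint.

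**Working it through.** The documents give no event count or power figure that bears on this rule, so there is no plan figure to reproduce. The check has three parts.

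**1. Timing.** The EoT visit is 0 to 28 days after discontinuation, and the next assessment is about 3 months (91 days) later.

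- Earliest nominal scan: 0 + 91 = day 91. Latest: 28 + 91 = day 119.
- With the ±14-day follow-up visit window (footnote b itself gives none for scans): 91 − 14 = day 77 to 119 + 14 = day 133.
- The earliest nominal scan would have to be 91 − 30 = 61 days early to fall inside the cut-off.

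An EoT scan, where one is done, falls inside. So could a 9-weekly scan that happened to be due soon after an early stop. No quarterly post-EoT scan does.

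**2. PFS events lost per 20 patients.** Inputs from the documents: 20 patients per arm (Protocol 6.1); median PFS 4.2 months (LEAP-004, Protocol 4.2) or 8.8 months (the earlier melanoma study, Protocol 4.3, which included CPI-naive patients). Assumptions:

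- Exponential PFS, with stopping unrelated to prognosis and no new therapy.
- Data cut C at 12, 18 or 24 months of follow-up.
- A share p stops before PD. The documents do not give p. Protocol 4.4 quotes discontinuation for TEAEs of 10% (QW) and 19% (BIW) in an ovarian study, a weak proxy; 30% is an assumed upper value.

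With λ = ln 2 / median, μ = λp/(1 − p) and δ = 30/30.44 = 0.986 months, the chance of stopping and then having PD or death more than 30 days later but before C is

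μ/(λ+μ) × exp(−λδ) × [1 − exp(−(λ+μ)(C−δ))] − exp(−λC) × [1 − exp(−μ(C−δ))].

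Example (median 4.2, p = 0.19, C = 18): λ = 0.1650, μ = 0.0387. First term 0.19 × 0.8499 × (1 − 0.0312) = 0.1564; second term 0.0247; difference 0.1317; × 20 = 2.63 events.

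| Median PFS (months) | p | Closed form, C = 12 / 18 / 24 | With scan schedule, C = 12 / 18 / 24 |
|---|---|---|---|
| 4.2 | 10% | 0.97 / 1.35 / 1.54 | 0.85 / 1.29 / 1.52 |
| 4.2 | 19% | 1.93 / 2.63 / 2.98 | 1.71 / 2.55 / 2.93 |
| 4.2 | 30% | 3.23 / 4.29 / 4.77 | 2.86 / 4.14 / 4.77 |
| 8.8 | 10% | 0.43 / 0.76 / 1.05 | 0.35 / 0.68 / 1.00 |
| 8.8 | 19% | 0.88 / 1.54 / 2.09 | 0.70 / 1.39 / 1.99 |
| 8.8 | 30% | 1.53 / 2.62 / 3.50 | 1.24 / 2.38 / 3.32 |

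The last column is a simulation of 200,000 patients with an EoT scan at day 28 after stopping and scans every 91 days from then on. If half of those who stop start new therapy first, the figures halve.

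**3. DOR.** At the cited ORRs of 21.4% (LEAP-004) and 31% (CPI-refractory patients in the earlier melanoma study), 20 × 0.214 = 4.28 and 20 × 0.31 = 6.2 responders are expected per arm. One responder is 1/4.28 = 23% or 1/6.2 = 16% of the DOR sample.

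**The case against.** **Rows 3 and 4 could still count the event.** PD on the first quarterly scan meets row 3 as written, and nothing says that row 5 overrides it. That ambiguity is real. It does not rescue the rule: row 5's new-therapy and database-cut limits work only if row 5 overrides rows 3 and 4. If the opposite was meant, the 30-day item does no work and two programmers could derive different PFS datasets. Either way the table needs an edit.

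**It may be a deliberate choice.** A 30-day limit takes in an EoT scan done within 28 days, so an analysis of treatment time plus the EoT scan is a plausible intent. The protocol sets almost no censoring rules of its own, and the endpoint definitions do not mention new therapy either. Such an analysis would be legitimate if declared and justified. Here it is neither, and the protocol schedules post-treatment scans specifically for PFS.

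**Lost events are not bias.** This stands. If stopping is unrelated to prognosis, as assumed above, Kaplan-Meier remains valid and the main cost is precision. In simulated 20-patient arms with an 18-month cut and no scan grid, row 5 moved the typical median estimate only from about 3.9 to 4.0–4.2 months (true value 4.2) and from about 8.2 to 8.5–8.8 (true value 8.8) as p rose from 10% to 30%. The worry about informative censoring is separate and has not been quantified.

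**The upper sizes are soft.** Also fair. The 19% comes from a BIW schedule that this trial does not use, and the 30% is assumed. How often responders will stop both drugs is unknown, since the protocol lets prolonged responders drop pembrolizumab and continue selinexor.

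**Conclusion.** The concern holds. On its coherent reading, row 5 removes from PFS and DOR every progression found at a quarterly post-EoT scan and every death more than 30 days after stopping. That contradicts the protocol's planned follow-up and is not declared in SAP 1.6.

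The timing conclusion needs no assumption beyond the protocol's own schedule. The size does: about 0.35 to 1.5 PFS events per 20-patient arm if 10% stop before PD, 0.7 to 3.0 at 19% and 1.2 to 4.8 at 30%, under the conditions listed in the check. No direction of bias is claimed.

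The effect is confined to two secondary endpoints and to patients who stop for reasons other than PD. ORR and OS are untouched. This should be fixed before database lock, but it does not threaten the primary analysis.

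**What to change.** In SAP Table 4-2:

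- Delete the 30-day post-discontinuation item from row 5. Count PD and death until new antineoplastic therapy, withdrawal of consent, loss to follow-up or database cut, subject to the existing missed-assessment rule.
- State that the remaining row 5 cut-offs take precedence over rows 3 and 4.
- State that missed assessments after EoT are counted against the 3-month schedule.
- Keep the 30-day version, if wanted, as a labelled sensitivity analysis, and define discontinuation for a regimen in which one drug may continue alone.

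If the sponsor prefers the 30-day rule as the main analysis, it should be justified, declared in SAP 1.6 and given explicit precedence. That would cure the undeclared departure but would still leave planned PFS scans unused.

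The cost is SAP wording and a small programming change. The scans are already in the protocol, so no new data are needed.

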5. SAFETY

All safety analyses will be reported by the actual treatment arm patients received and overall, among patients in the safety population.

Safety analyses will be based on the reported AEs and other safety information, such as clinical laboratory assessments including hematology and serum chemistry, vital signs, and physical examination.

The observation period will be divided into the following periods:

- The pre-treatment period is defined as the time from the signed informed consent date up to first dose of study treatment.
- The treatment period is defined as the time from first dose of study treatment to last dose of study treatment + 30 days inclusive, or start of new anti-neoplastic therapy exclusive, whichever occurs first.
- The post-treatment period is defined as the time beyond the treatment period.

All safety analyses will be performed using the following common rules:

- Safety data in patients who do not belong to the safety population (e.g., enrolled but did not receive any dose of study treatment, partial or complete) will be listed separately.
- The baseline value is the last available value before the first dose of study treatment.
- The analyses of the safety variables will be descriptive, and no systematic statistical testing is planned.

5.1. Adverse Events

An AE is defined as any undesired medical occurrence in a patient receiving a pharmaceutical product regardless of a causal relationship with this treatment. An AE can therefore be any unfavorable sign and unintended sign (including an abnormal laboratory finding), symptom, or disease temporarily associated with the use of a study treatment, whether or not related to the study treatment.

All AEs (including serious adverse events [SAEs]) will be coded to a Preferred Term (PT) and associated primary System Organ Class (SOC) using the Medical Dictionary for Regulatory Activities (MedDRA).

The severity of all AEs will be graded according to the Common Terminology Criteria for Adverse Events (CTCAE) grading scale. The severity of the AE is different from the seriousness of the AE. For AEs not covered by CTCAE, the severity will be characterized as "mild," "moderate," "severe", "life-threatening" according to the following definitions:

- Mild events are usually transient and do not interfere with the patient's daily activities.
- Moderate events introduce a low level of inconvenience or concern to the patient and may interfere with daily activities.
- Severe events interrupt the patient's usual daily activities.
- Life-threatening.

5.1.1. Definitions of Treatment-Emergent Adverse Events (TEAEs), Serious Adverse Events (SAEs), and Treatment-Emergent Treatment-Related Adverse Events (TRAEs)

5.1.1.1. Treatment-Emergent Adverse Event (TEAE)

Treatment-emergent adverse events (TEAEs) are defined as any event that was not present prior to the initiation of study treatment or any event already present that worsens in either intensity or frequency following exposure to study treatment, i.e., from the date of first study treatment up to the date of last study treatment + 30 days inclusive (or the day before initiation of a new antineoplastic treatment, whichever occurs first). Additionally, TEAEs also include any event that developed post the treatment period but was assessed by the Investigator as related to study treatment.

